Milestone 1: NF loci (dACC or amygdala) must show higher activity during ESF-NF and higher FC with mPFC after NF training during the ESOM or ER tasks with effect sizes of $d \geq 0.4$.

Milestone 2: 20% of variance in psychological target's change (ETB, IAT) must be associated with amygdala or dACC to mPFC FC changes during the ESOM or ER tasks after NF.

If those milestones are met, during **the R33 phase**, 70 suicide attempting participants with pre-NF assessments will be randomized 1:1 to: NF or NF from a region that is not related to memory recall, labeled as "Unrelated-NF". Participants will be matched in sex, age, IQ, illness severity, suicide ideation, and abuse history if possible. Leveraging Bayesian methods to increase power, our aims and hypothesis (**H**) for the R33 phase are:

R33 Aim 1. Confirm target engagement in the NF versus the Unrelated-NF group.

H1.1: Right amygdala or dACC activity will be higher for active versus Unrelated-NF.

H1.2: Right amygdala or dACC – mPFC FC will be higher during self-processing and affect regulation tasks following active NF compared to Unrelated-NF training sessions.

R33 Aim 2. Test the relationship between neural and psychological targets' engagement and suicide ideation. H2.1: Lower affect dysregulation and abnormal self-processing behavior will follow active NF as compared to Unrelated-NF, mediated by amygdala or dACC to mPFC FC changes in self-processing and affect regulation tasks. H2.2: Higher amygdala or dACC to mPFC FC after NF will be associated with lower suicide ideation. H2.3: Affect dysregulation or abnormal self-processing behavioral changes will mediate the association between changes in FC and suicide ideation before versus after NF.

2. Background

Suicide is the 2nd leading cause of adolescent death in the U.S ²¹. Yet it is increasingly acknowledged that current evidence-based interventions for illnesses linked to suicide ideation and attempts underperform across the lifespan ^{1-7,22}.

3. Study Endpoints/Events/Outcomes

3.1 Primary Endpoint/Event/Outcome:

The primary outcome of the R61 stage will be the fMRI imaging results, behavioral tasks (IAT and EBT) and self-reported suicide ideation data. The DERS²³, RD¹²⁰ and the SPPA^{24,25} will provide self-report measures of affect dysregulation and abnormal self-processing. **The primary outcomes of the R33 stage** are similar as above but now include the C-SSRS⁹⁸ and SIQ²⁹ to test changes in suicide ideation and attempts

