
- 4.1 Drug/Device Handling: NA
- 4.2 Biosafety: NA
- 4.3 Stem Cells: NA
- 4.4 Fetal Tissue: NA

5. Procedures Involved

Study Design: After securing a permission to contact from participants or parents, study personnel will screen suitability (See **Phone Script**) with parents or legal representatives over the phone before scheduling the first session. Participants will be assessed in person ~2 weeks before and after NF training (Day 1: first session) and ~1 month after the last NF training. The first session visit can occur at the department of psychiatry, at the inpatient unit where the participant might still be interned, or in the same building where the patient unit is at (with permission of the leadership in the inpatient unit and provided that a secure confidential room is available).

Two to three weeks can pass between each visit. Responses from parents and clinicians might also be used for preliminary screening of participants and their families over the phone, to establish eligibility for in-person assessments. **Table 1** provides the sequence of key events. **To confirm inclusion and enable brain-behavior analyses, disorders will be established by clinicians administering the new computerized KSADS-COMP or the K-SADS-PL²⁶ interview version lead by a trained staff member.** The BDI²⁷ and CTQ²⁸ will yield additional dimensional depression and PTSD indexes. The C-SSRS⁹⁸ and SIQ²⁹ will confirm suicide ideation and attempts at baseline. The DERS²³, RD¹²⁰ and the SPPA^{24,25} will provide self-report measures of affect dysregulation and abnormal self-processing. Participants will also complete the IAT^{38,39} a behavioral task of abnormal self-processing and the Emotional Testing Battery (ETB), which measures affect regulation and self-processing⁴⁰ outside the scanner. After concluding the 1-month follow-up participants that accept remaining in touch with the experimenters may be called for

another follow-up brief phone interview and/or to be invited to other studies. This optional follow-up involves administering a few previously approved questionnaires that will measure depressed mood, feelings, suicidal thoughts and/or suicidal feelings since they last participated. **Before and after the NF training participants will complete the following tasks or alternative tasks that measure the similar constructs of affect regulation and self-processing. The following tasks are exemplars of what the participant will experience.**

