Visit 1: Baseline	Visit 2: Scan day 1	Visit 3: Scan day 2	Visit 4: Post-NF	Visit 5: Approximately 1 Month later after Visit 4.	Additional visits as needed to complete pending tasks
KSADS. Children Depression Rating Scale-Revised (CDRS). Difficulty with Emotion Regulation Scale (DERS) ²³ . Self-Perception Profile for Participants (SPPA) ^{24,25} . Responses to Depression (RD) ⁴⁸ : rumination.	SIQ, BDI, DERS, SPPA, RD Medication, psychotherapy. Review 5 happy memories.	SIQ, BDI, DERS, SPPA, RD Review 5 happy memories.	SIQ, BDI, DERS, SPPA, RD.	SIQ, BDI, DERS, SPPA, RD Online	Anything pending
Columbia-Suicide Severity Rating Scale, C-SSRS, ⁴⁹ . Suicide Ideation Questionnaire, SIQ ²⁹ .	ESOM: 14 min ER: 13 min	NF Training: ESF_NF ~ 44.32 min	C-SSRS, CDRS	KSADS-COMP and C-SSRS	Anything pending
Beck Depression Inventory, BDI ²⁷ . Child Trauma Questionnaire, CTQ ²⁸	NF Training: ESF_NF~ 44.32 min	ESOM: 14 min ER: 13 min	IAT and ETB		Anything pending
Wechsler Abbreviated Scale for Intelligence, WASI ⁵⁰ . Edinburgh handedness inventory. Write/ discuss 5 happy memories.	30 min break	30 min break	Medication, psychotherapy	Medication and psychotherapy	Anything pending
Medication, psychotherapy, demographics, and puberty stage⁵¹.					Anything pending
Implicit Association Test (IAT): Abnormal Self-Processing Behavior ^{38,39} . Emotional Testing Battery (ETB): Affect and self-processing ⁴⁰ , or another similar test. Can be administered also before scanning on scan day 1 or after scanning on scan day 2.	Ease of recall rating. SIQ, BDI, DERS, SPPA, RD.	Medication, psychotherapy. Ease of recall rating. SIQ, BDI, DERS, SPPA, RD.		IAT and ETB	Anything pending

- Items from the KSADS, C-SSRS and Medication and psychotherapy forms will be shared with the IMM to confirm inclusion vs. exclusion of participants.

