7.2 Sharing of genetic testing: **N/A.**

8. Study Population

8.1 Inclusion Criteria:

a) 1st-time suicide attempting participants (**11-18 years**) with current suicide ideation. However, if within the first 3 months of the project starting participant recruitment it is difficult to recruit the targeted number of participants, **the study population will be expanded to any suicide attempting participants without restricting to 1st time attempters, and we could also include first time attempters with low or no suicide ideation.** This flexibility to recruitment criteria is implicit in our protocol if recruiting 1st time attempters with lingering ideation proves to be very difficult.

We will also include participants with any level of depression and: 1. current suicide ideation, 2. no current suicide ideation but a history of past suicide ideation, 3. neither past nor present suicide ideation.

History of suicide attempts, suicide ideation, and depression levels will be ascertained during the phone screening. During the first session, suicide ideation levels will be ascertained using the suicide ideation questionnaire or a similar approved short questionnaire. Any criteria not specifically coded for by the BPIC will be tested by study and the research staff, e.g., IQ and handedness. If targeted clinical population participants become 18 during the project, they will be re-consented with the adult consent form.

b) Adult individuals (18 -45 years old) with Borderline Personality Disorder (BPD) symptoms or youth with BPD traits (17yrs.) regardless of their history of suicide ideation or attempts.

8.2 Exclusion Criteria: Please see Table 2.

Table 2. Inclusion and Exclusion Criteria	
Inclusion R61-R33	Exclusion R61-R33

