
a) 11-18 years old, right or left-handed, gender balanced participants. Depressive Disorders, PTSD.
 
1. Suicide ideation ~1 standard deviation in the suicide ideation questionnaire ²⁹ and/or a suicide attempt (within the last year or at any time in their life).
 
2. Depressed participants regardless of their history of suicide attempts with any current or past levels of suicide ideation. Comorbid anxiety disorders, eating disorder symptoms & experimental substance use allowed. Stable medication and therapy allowed (~ 2 weeks of treatment), however the latter can be relaxed to increase accrual.
	
MRI contraindicated (e.g., claustrophobia or pacemakers or other metal implants incompatible with MRI). History of traumatic brain injury. IQ<75. Severe or acute medical illnesses that require multiple hospitalizations. History of severe brain damage, frequent/current seizures, mental retardation, or serious neurological disorder that affects brain structure. Previous history or current diagnosis of Schizophrenia, or Autism. Refusal to cooperate with study procedures. High acute, imminent suicide attempts risk. Please see the Suicide Risk Assessment section for criteria to determine this risk. [name], and [name], PhD. will consult each other and triage the need for hospitalization, emergency room escort, and medication adjustment for participants with acute suicide risks. An additional level of safety may include “on-call” mental health workers that staff can consult to determine exclusion.
 
A current diagnosis of a substance use disorder. Primary psychotic disorder or active psychosis. Active substance abuse disorder or primary diagnosis of anorexia disorders. Symptoms of anorexia disorders are not considered exclusionary criteria.

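### The plan does not say which pre-neurofeedback score is the reference for ideation and self-report change; using the Visit 1 SIQ could build regression to the mean into the uncontrolled R61 change, and a Visit 2 pre-scan score is already scheduled

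*Combined protocol and SAP*

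**What the plan says.** **Entry.** Section 8.1 provides for ideation to be assessed at the first session: "During the first session, suicide ideation levels will be ascertained using the suicide ideation questionnaire or a similar approved short questionnaire". Table 2 gives one adolescent route as "Suicide ideation ~1 standard deviation in the suicide ideation questionnaire", but the same sentence continues "and/or a suicide attempt (within the last year or at any time in their life". A second route takes "Depressed participants regardless of their history of suicide attempts with any current or past levels of suicide ideation". Section 8.1 also admits depressed participants with "no current suicide ideation but a history of past suicide ideation, 3. neither past nor present suicide ideation", and the borderline personality cohort enters whatever its ideation history. Sections 8.1 and 9 allow screening by phone, and section 9 allows a questionnaire other than the SIQ.

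**Visit 1.** Table 1 labels it Baseline, and section 3 has the SIQ and C-SSRS confirm ideation at baseline. Section 5 (Study Design) places an assessment about two weeks before NF, lets the first session take place "at the inpatient unit where the participant might still be interned", and allows two to three weeks between visits.

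**Visit 2.** Above the scan tasks and the first NF session, Table 1 lists "SIQ, BDI, DERS, SPPA, RD Medication, psychotherapy. Review 5 happy memories". The same five questionnaires are listed again after NF. The note introducing Table 1 allows the order and day of procedures to change.

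**R61 outcome and design.** Section 3.1 includes "self-reported suicide ideation data" in the R61 primary outcome. Sections 1 and 29.1 describe two active loci with random assignment between them; the Unrelated-NF arm appears only in R33.

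**Analysis.** Section 18 correlates connectivity with change in ETB, IAT, DERS, SPPA and RD from before to after training. It specifies ideation models only for R33 (H2.2, H2.3). It does not say which of the pre-NF scores is the one before training.

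**The concern.** When people enter because a noisy score is high, their next score tends to be lower without any intervention. If that same score is also the starting point for change, the fall is counted as change over training. Recovery in the weeks between Visit 1 and the first NF session would be added to it.

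R33 has a randomised Unrelated-NF arm, so the expected artefact is the same in both arms and drops out of the comparison between them. R61 has no such protection for a within-group change: randomisation between two active loci protects only the comparison of one locus with the other.

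What is at stake is how an R61 ideation result would be read and reused. Ideation is a named primary outcome, section 18 contemplates using R61 results to adjust R33 models, and section 21 provides for sharing results. With several eligible pre-NF scores and none chosen, the reference could also be picked after the data are seen.

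**Working it through.** **The plan's own figure.** The documents give no figure for SIQ change or SIQ retest correlation. The only R61 power figure is 80% at d = 0.49 with 20 per locus, given for target engagement. A one-sample t-test with n = 20 at two-sided 0.05 has 54.8% power at that effect, and at least one of two independent loci gives 1 − (1 − 0.548)² ≈ 0.80. So it reproduces on that reading, but it has no bearing on ideation.

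**Inputs.** From the documents: a cut at about 1 SD on the SIQ (reference norm and direction not stated), 20 per locus, SIQ at Visit 1, at Visit 2 before NF, and after NF. Assumed: standardised normal scores, no NF effect, retest correlation r from 0.6 to 0.8, and a share f of participants entering through a cut at +1 SD, the rest unselected.

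**Formula.** The mean score above the cut is E[z | z > 1] = φ(1)/(1 − Φ(1)) = 1.525. The expected fall from Visit 1 by regression alone is f × 1.525 × (1 − r).

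| Share f | r = 0.8 | r = 0.7 | r = 0.6 | Significant fall at n = 20 |
|---|---|---|---|---|
| 1 (upper case) | 0.31 SD | 0.46 SD | 0.61 SD | 57% to 88% |
| 0.5 | 0.15 SD | 0.23 SD | 0.31 SD | about 16% to 28% |
| 0.25 | 0.08 SD | 0.11 SD | 0.15 SD | about 7% to 10% |
| 0 | 0 | 0 | 0 | 2.5% (nominal) |

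The last column is the chance that a two-sided 0.05 paired t-test shows a fall when NF does nothing. The plan specifies no such R61 test, so this column only illustrates the scale.

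**Sensitivity to the cut.** If the 1 SD refers to a community norm and the source population scores higher, selection is milder. With everyone selected and the cut at the source mean, E[z | z > 0] = 0.798 and the fall is 0.16 to 0.32 SD. With the cut one SD below the mean, E[z | z > −1] = 0.288 and the fall is 0.06 to 0.12 SD.

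**From the Visit 2 score instead.** The expected fall from Visit 2 to post-NF is f × 1.525 × (r12 − r14), where r12 and r14 are the correlations of Visit 1 with Visit 2 and with the post-NF visit.
- Equal correlations: 0 SD, and the false-positive rate returns to about 2% to 3%.
- Decaying correlations, r12 = 0.8 and r14 = 0.6, with f = 1: 1.525 × 0.2 = 0.31 SD remains of the 0.61 SD from Visit 1.

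**R33 covariate.** Residual variance of the post score, as a fraction of its total variance:
- Equal correlation r: one baseline leaves 1 − r²; the mean of two leaves 1 − r²/((1 + r)/2). The ratios are 0.86, 0.83 and 0.80 at r = 0.6, 0.7 and 0.8, so averaging helps.
- Decay (r12 = 0.8, r14 = 0.6, r24 = 0.7, where r24 is Visit 2 to post): the mean leaves 1 − 0.65²/0.9 = 0.531, against 1 − 0.7² = 0.510 for Visit 2 alone, 4% more. At r24 = 0.8: 1 − 0.7²/0.9 = 0.456 against 0.360, 27% more.
- Both scores as separate covariates under the same decay: 1 − (0.36 + 0.49 − 0.672)/0.36 = 0.506, and 1 − (0.36 + 0.64 − 0.768)/0.36 = 0.356. Neither is worse than Visit 2 alone.

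**The case against.** The strongest reply is that this is an unstated reference, not a demonstrated bias. Most of that stands:

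- A reader might infer that Visit 1 is the planned reference for ideation change. Baseline is a visit label, and the SIQ's stated role there is to confirm ideation; no section expressly makes it the reference.
- A reader might infer that all participants are selected on a high Visit 1 SIQ. An attempt at any time in life is enough, as is depression with any or no ideation, and screening may be done by phone or on another questionnaire. Selection through the SIQ cut may be rare.
- A reader might infer that Visit 1 often falls in or just after a crisis. The inpatient unit is permitted as a setting, but no frequency is given, and people at imminent risk are excluded.
- A reader might infer that R61 will report a false ideation benefit or pass its milestones because of one. No R61 ideation test is specified, and the milestones use NF activity, connectivity, ETB and IAT.
- Visit 2 is not a complete cure. If correlations decay with time, part of the regression remains.

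The reply does not dispose of the point. Ideation is a named R61 primary outcome, the label and the two-weeks-before timing steer an analyst towards Visit 1, and a later score is already scheduled on the same day as the pre-NF connectivity measure. Naming it is a real gain for little effort.

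**Conclusion.** The concern holds as an undefined reference with a risk attached. If the Visit 1 SIQ is used, the uncontrolled R61 ideation change can include regression to the mean and pre-training recovery. The regression part runs from about 0 SD if few enter through the SIQ cut, through 0.15 to 0.31 SD if half do, to 0.31 to 0.61 SD as an upper case if all do. These figures rest on an assumed r of 0.6 to 0.8, a cut at +1 SD of the source distribution, and no NF effect. Recovery before training would add an amount the documents do not allow to be estimated.

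The documents do not support extending this to the R61 go/no-go decision or to the R33 comparison between arms.

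**What to change.** 1. Define the pre-NF reference for SIQ, BDI, DERS, SPPA and RD as the Visit 2 administration, completed before the first NF run. This puts it on the same day as the pre-NF connectivity measure.
2. In R61, report the Visit 1 to Visit 2 change beside the post-NF change as drift without training, and state that R61 ideation change is descriptive.
3. In the R33 ideation models, adjust for the Visit 2 pre-NF score. Add the Visit 1 score as a separate covariate if wanted, not as a forced average.

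**Cost.** No new data: a few sentences in section 18, plus a rule that the Visit 2 questionnaires precede NF despite the flexible ordering allowed with Table 1 and the remote options in section 5. The R61 ideation change will probably look smaller.

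**Limits.** This reduces regression to the mean but may not remove it if correlations decay, and it does not deal with later recovery or concurrent treatment. It does not reach the C-SSRS, which is scheduled at Visits 1, 4 and 5 but not at Visit 2.
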